
2 STUDY DESIGN

2.1 OVERALL DESIGN

Primary Purpose : Prevention

Allocation : Randomized

Interventional Model : Parallel Assignment

Interventional Model Description: In a longitudinal study design, 40 participants with chronic SCI will be randomly assigned to one of the two study groups (HIIT and control) in a 1:1 ratio. Randomization will be performed using the block randomization method. Randomization will be performed using the block randomization method. A randomization list will be generated and assignments will be placed into

closed envelopes and given to each study participant. Participants will be assessed at baseline and 16-wks post HIIT or control

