7.2 SAMPLE SIZE DETERMINATION

40 participants will be randomized to home-based HIIT exercise or a no-exercise control group for 16-weeks.

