7.3 STATISTICAL ANALYSES

Descriptive statistics, such as means, standard deviations, and 95% confidence intervals, will be calculated for all study variables of interest. The primary method of analysis will be mixed models repeated measures analyses, such as repeated measures analysis of covariance. This will allow us to test the group, time, and group by time interaction effect simultaneously. An appropriate structure for the covariance matrix (e.g. the unstructured covariance matrix) will be selected for these models using the final data. The Tukey-Kramer multiple comparisons test will be used as the *post hoc* test of choice for these analyses. ***Biological variables, such as age, sex, race, and %fat, will be accounted for in these models (see Rigor and Reproducibility in Statistical Design and Power document for details)*** Overall comparisons between means of the two groups will be performed using the two-group t-test, and overall changes within groups will be examined using the paired t-test. Correlation analysis will be performed, with Pearson correlation coefficients being calculated for pairs of continuous variables. Distributions of continuous variables will be examined for normality using box plots, stem-and-leaf plots, and normal probability plots; those deviating greatly from a normal distribution will be log transformed or analyzed using appropriate nonparametric tests such as the Wilcoxon rank-sum and signed-rank tests. Multiple imputation methods may be used to address missing data for variables with moderate amounts of missing data ($\geq 10\%$) and after examining whether data are missing completely at random (MCAR), at

random (MAR), or not at random (MNAR). Statistical tests will be two-sided and will be performed using a 5% significance level. SAS software, version 9.4 or later, will be used to conduct the statistical analyses.

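### Section 7.3 does not name the treatment contrast, and its post hoc and within-arm tests do not supply one

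*Combined protocol and SAP*

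**What the plan says.** The design is simple. Section 2.1 assigns participants to "one of the two study groups (HIIT and control) in a 1:1 ratio", and "Participants will be assessed at baseline and 16-wks post HIIT or control". Section 7.2 gives the size: "40 participants will be randomized to home-based HIIT exercise or a no-exercise control group for 16-weeks". That is 20 per arm and four arm-by-visit means.

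Section 7.3 sets out the analysis. "The primary method of analysis will be mixed models repeated measures analyses, such as repeated measures analysis of covariance". On what the model tests, it says: "This will allow us to test the group, time, and group by time interaction effect simultaneously". It continues: "The Tukey-Kramer multiple comparisons test will be used as the" post hoc test for these analyses, without saying which means are compared. It then adds two-group t-tests between the arms and says that "overall changes within groups will be examined using the paired t-test". On the error rate: "Statistical tests will be two-sided and will be performed using a 5% significance level".

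The covariates given as examples are age, sex, race and percent fat. An endpoint's own baseline value is not among them, except that percent fat may serve that purpose for body fat itself. No sentence says which of these tests gives the treatment effect, or that an estimate of it will be reported with a confidence interval.

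**The concern.** A reader of section 7.3 meets four kinds of test on the same data: the model effects, the post hoc comparisons, the two-group t-tests and the paired t-tests. Only a comparison of the arms answers the trial's question. The post hoc step and the paired tests can produce p-values that do not address it, and nothing in the section ranks the model's interaction above them.

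Two things are at stake. One is a claim of benefit resting on a significant change in the HIIT arm beside a non-significant change in the control arm, which is not evidence that the arms differ. The other is precision. Of the contrasts available from data the trial already collects, the section does not commit to the most precise one.

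**Working it through.** The plan states no power, effect size, SD, correlation or critical value, so it has no figure to reproduce.

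**Inputs from the documents.** Two arms, 1:1, 40 participants (20 per arm); two visits; two-sided 5%.

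**Assumptions.** Residual df of 38 (40 completers, no covariates). True effect of 0.5 SD of the endpoint. Baseline to week-16 correlation r of 0.6, 0.8 or 0.9. Equal SD at both visits.

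**1. The interaction is the treatment effect.** In a 2 x 2 layout the group-by-time contrast is (HIIT week 16 − HIIT baseline) − (control week 16 − control baseline). It has one degree of freedom. In one simulated data set of 40 complete cases, the mixed-model interaction t and the two-sample t on change scores were both 2.436.

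**2. What Tukey-Kramer does.** Its critical value on the t scale is q(0.95; k, df)/√2.
- k = 2 (two arms, two visits, or two adjusted week-16 means): 2.024, against t(0.975; 38) = 2.024. The ratio is 1.000, so the procedure adds nothing.
- k = 4 (all arm-by-visit means): 2.686 against 2.024. The ratio is 1.327, equivalent to a per-comparison level of about 0.0107. The ratio is 1.333 at 28 df and 1.319 at 76 df, so the choice of df matters little.

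The six pairs of the four means are one baseline difference, one week-16 difference, two within-arm changes and two cross pairs. Each involves two means. The difference in change involves all four, with weights +1, −1, −1, +1, so no pair equals it.

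**3. The paired t-tests.** Suppose both arms change by the same amount, δ SDs of the change score, so the true treatment effect is zero. Each arm's paired test has 19 df and noncentrality δ√20. If p is its chance of significance, the chance that HIIT is significant and control is not is p(1 − p).

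| δ | p | p(1 − p) |
|---|---|---|
| 0.3 | 0.247 | 0.186 |
| 0.4 | 0.397 | 0.239 |
| 0.5 | 0.565 | 0.246 |
| 0.6 | 0.721 | 0.201 |

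The range is about 19% to 25%.

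**4. Which contrast to name.** With endpoint SD 1, the change score has SD √(2(1 − r)). The week-16 value adjusted for its own baseline has SD √(1 − r²). The noncentrality is (0.5/SD) × √(20/2), with 38 df for the change score and 37 df after baseline adjustment.

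| r | SD, change | Power, change | SD, adjusted | Power, adjusted |
|---|---|---|---|---|
| 0.6 | 0.894 | 41% | 0.800 | 49% |
| 0.8 | 0.632 | 68% | 0.600 | 73% |
| 0.9 | 0.447 | 93% | 0.436 | 94% |

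The two contrasts target the same effect in a randomized trial but are not the same estimator. The adjusted one is more precise at every r shown.

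**The case against.** The strongest reply is that the plan already tests the right thing. The mixed model is the primary method, it includes the group-by-time interaction, and the level is 5%. Tukey-Kramer is only a post hoc step and leaves that test as it is. This stands: the treatment comparison is neither missing nor subject to an inflated critical value.

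A reader might infer that Tukey-Kramer raises the bar for the trial's main question by a third. The documents do not support that. Section 7.3 never says that the four arm-by-visit means are compared, and on two means there is no inflation. The section refers to a separate document on rigor and power for covariate details; that document is not available here, and whether it defines contrasts is unknown.

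A reader might also set the 68% power of the difference in change (r = 0.8) against the 15% power of a Tukey-adjusted week-16 pair and blame Tukey-Kramer for the gap. Most of it has another cause. The week-16 comparison that ignores baseline has noncentrality 0.5 × √10 = 1.58 and power of 34% at the ordinary critical value. So 68 − 34 = 34 points come from ignoring baseline and 34 − 15 = 19 points from Tukey-Kramer. Even those 19 are lost only if the conclusion is drawn from that pair, which the plan does not say.

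Nor is the misleading within-arm pattern a product of Tukey-Kramer. At a shared change of 0.3 SD it occurs about 9% of the time with the Tukey critical value against 19% with paired t-tests; at 0.6 SD it is 25% against 20%. The source is testing within arms. It is fair to add that section 7.3 presents the paired tests as a look at changes, not as the basis for an efficacy claim. But it does not exclude that use.

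**Conclusion.** The point holds as a gap in specification. Section 7.3 does not say which contrast is the treatment effect, and it carries tests that cannot supply one. Tukey-Kramer is redundant on two means. If used on the four arm-by-visit means, its pairs are not the difference in change and its critical value is 2.69 against 2.02. The planned interaction test is unaffected either way.

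The paired t-tests carry a 19% to 25% chance of a misleading pattern when both arms change equally by 0.3 to 0.6 SD of the change score. That range is an assumption, since the documents give no expected change in the control arm.

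Naming the baseline-adjusted contrast gains about 8, 5 and 1 percentage points of power at r = 0.6, 0.8 and 0.9. These figures assume a 0.5 SD effect and 20 completers per arm. Dropout would lower all the powers, and the correlation may differ between endpoints. The gain is modest but free.

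**What to change.** In section 7.3, name one treatment contrast for each endpoint: the HIIT-minus-control difference at week 16, adjusted for that endpoint's own baseline value. Report it with its 95% confidence interval at the ordinary t critical value. Do not describe it as interchangeable with the group-by-time contrast on change scores; choose one in advance, and the adjusted one is the more precise.

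Delete the Tukey-Kramer sentence. Replace the paired t-tests with within-arm mean changes and confidence intervals, given descriptively and without p-values. State that the two-group t-tests are not a second test of the treatment effect.

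The cost is a change of wording in one section. It needs no new data or visits, and slightly less analysis.

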1.2 STUDY RATIONALE

For individuals with spinal cord injury (SCI), exercise participation reduces the risk of developing chronic cardiometabolic diseases, which are leading causes of rehospitalization and death within this population. Accordingly, recent SCI exercise guidelines have highlighted a need for exercise trials that can improve cardiometabolic factors such as glucose tolerance, blood lipids, blood pressure, and body composition. However, to date, the number of exercise trials examining these cardiometabolic outcomes in SCI is low, and these exercise regimens are often inconvenient for individuals with SCI to perform within their community. In addition to the functional impairment associated with the disability, individuals with SCI experience a number of barriers to exercise participation, such as lack of time (e.g. conflict with work schedule), accessible or usable equipment and facilities, and transportation. Thus, it is important to identify effective modes of exercise that can improve overall health but do not require a significant overall weekly time commitment. Investigators recently demonstrated that individuals with SCI could safely perform high intensity interval training (HIIT) using arm crank cycling and that as few as two days per week of HIIT could improve cardiometabolic health. Despite the advantages of HIIT, it is important to identify methods of implementing exercise trials that can successfully reach and maintain participation in larger cohorts. Recent work by the investigative group demonstrated that individuals with SCI expressed favorable perceptions of home-exercise training that incorporated telehealth technology, which allowed a fitness specialist to remotely monitor participants' training progress in real-time and provide verbal support via videoconferencing. This method of training holds even greater value for home-exercise programs that require monitoring to dose-specific protocols such as HIIT. However, the long-term success of HIIT will greatly depend on the ease at which the program can be implemented, as well as participants' adherence and perceptions of using the technology, which has not been investigated in SCI. The goal of this study is to integrate a home-based telehealth HIIT arm crank exercise training program in individuals with SCI and assess changes in cardiometabolic health and physical function. The secondary goal is to explore the uptake and implementation of HIIT in SCI. 40 participants will be randomized to home-based HIIT exercise or a no-exercise control group for 16-weeks. Body composition, aerobic fitness, muscular strength, and changes in cardiometabolic health will be assessed at baseline and 16-weeks post training. In addition to changes in cardiometabolic health outcomes, the investigators will also conduct interviews with participants to determine overall perceptions of the program, program likes and dislikes, perceived satisfaction and value, usability of equipment and technology, and factors that influence adherence.

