 - Laboratory analyses. Concentrations of blood lipids will be determined in the Core Laboratory of the CCTS, NORC, and DRC.
- Change in Body Composition [Time Frame: baseline]

- Dual-energy X-ray absorptiometry (DXA). Total and regional body composition will be measured by DXA (Lunar Radiation Corp., Madison, WI) at the Lakeshore Foundation Research Facility.
- Change in Body Composition [Time Frame: 16weeks post training]
 - Dual-energy X-ray absorptiometry (DXA). Total and regional body composition will be measured by DXA (Lunar Radiation Corp., Madison, WI) at the Lakeshore Foundation Research Facility.
- Change in Blood Pressure [Time Frame: baseline]
 - Systolic and Diastolic blood pressure will be assessed using standard blood pressure cuff and a stethoscope.
- Change in Blood Pressure [Time Frame: 16weeks post training]
 - Systolic and Diastolic blood pressure will be assessed using standard blood pressure cuff and a stethoscope.
- Secondary Efficacy Endpoint(s):

Semi-Structured Interview [Time Frame: 16 weeks post-training]

The semi-structured interviews will contain seven open-ended questions related to the following areas: 1) overall perceptions of the program, 2) program likes, 3) dislikes, 4) perceived satisfaction and 5) value, 6) technology and equipment usability, and 7) factors that affected adherence. These areas will be probed in greater detail by the interviewer through additional follow-up questions.

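### Does leaving the time point of the %fat covariate unstated in section 7.3 put the primary models at risk?

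*Combined protocol and SAP*

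**What the plan says.** Section 7.3 makes mixed-model repeated measures the primary method, testing group, time and group by time. On covariates it says that "Biological variables, such as age, sex, race, and %fat, will be accounted for in these models", and the sentence then refers the reader elsewhere: "see Rigor and Reproducibility in Statistical Design and Power document for details". That document is not among those supplied. On the covariance it says "An appropriate structure for the covariance matrix (e.g. the unstructured covariance matrix) will be selected for these models", with the choice made on the final data. It also plans unadjusted tests: "Overall comparisons between means of the two groups will be performed using the two-group t-test".

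Section 7.1 lists, among the primary efficacy endpoints, "Change in Body Composition [Time Frame: 16weeks post training" with a matching baseline entry, and describes the method: "Total and regional body composition will be measured by DXA". Section 1.2 confirms both assessments: "Body composition, aerobic fitness, muscular strength, and changes in cardiometabolic health will be assessed at baseline and 16-weeks post training". The documents do not name %fat as an endpoint. That it is one of the DXA measures is a fair inference, since DXA is the only body-composition method described.

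**The concern.** Randomised training cannot alter age, sex or race, but it may alter %fat. Section 1.2 cites a need for exercise trials that "improve cardiometabolic factors such as glucose tolerance, blood lipids, blood pressure, and body composition". In a repeated-measures model, a variable measured at both visits is easily entered visit by visit, and the wording of 7.3 does not forbid it.

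Adjusting for a post-randomisation value would change what the primary model estimates. For lipids, insulin sensitivity or blood pressure, the group-by-time term would become an effect with %fat held fixed. For fat mass, most of the effect could vanish. For %fat itself, the covariate would equal the response and the term would be zero by construction.

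The baseline reading also looks awkward in one place. When %fat is the outcome, its baseline value would be both a response and a covariate.

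**Working it through.** The documents give no effect size, SD or power on this point, so there is no figure of the plan's to reproduce. The inputs taken from them are 40 participants (7.2) at 1:1 (2.1), hence 20 per arm; two visits (1.2); and two-sided 5% tests (7.3). Everything else below is assumed. F is %fat, G is the arm, and d is the group-by-time term.

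**1. Baseline %fat, another outcome.** The model is Y0 = a + cG + bF0 + e0 and Y1 = a + t + (c + d)G + bF0 + e1. Subtracting gives

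Y1 - Y0 = t + dG + (e1 - e0).

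F0 drops out. The regressors for the change are a subset of those for baseline, so with complete data the joint fit returns the difference between arms in mean change. In the three simulated cases compared run by run, the estimates with baseline %fat and with no %fat differed by at most 5e-15.

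**2. Baseline %fat, %fat as outcome.** Now Y0 = F0, so b = 1 fits the baseline visit exactly. In an iterated unstructured fit, the baseline residual variance fell from 1.8e-3 (first iteration) to 2.8e-11 (fourth) and 2.6e-24 (ninth), and the matrix was singular at the eleventh. The equation for the change is the same as in step 1. In one simulated data set with 20 per arm:

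- Compound symmetry: determinant 0.012, estimate -0.690, SE 0.147, identical to the plain difference in change.
- Unstructured: estimate -0.690 and SE 0.147 through seven iterations, while the baseline variance collapsed.

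The covariate is redundant here. The difficulty lies in fitting one candidate covariance structure, and the answer is not distorted.

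**3. Visit-specific %fat, another outcome.** Subtracting now leaves b(F1 - F0) in the equation, so

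d = total effect - b x (shift in %fat).

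With an assumed total of -0.50 SD and the same slope b between and within persons:

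| Shift | b | d by formula | Simulated d (rejection) | With baseline %fat |
|---|---|---|---|---|
| -0.25 | 0 | -0.50 | -0.496 (51%) | -0.496 (52%) |
| -0.25 | 0.5 | -0.50 + 0.125 = -0.375 | -0.382 (42%) | -0.505 (59%) |
| -0.50 | 0.5 | -0.50 + 0.25 = -0.25 | -0.251 (20%) | -0.502 (59%) |

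The simulations used 2,000 runs per case, complete data, a correlation of 0.9 between visits for %fat and a residual correlation of 0.7.

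**4. How far those sizes can be trusted.** They depend on the common slope. With the shift at -0.50 and the slopes separated:

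- Between 0.5, within 0 (nothing acts through %fat): d is about -0.31 to -0.32, so there is bias without mediation. At -0.32 the pooled slope is (0.50 - 0.32)/0.5 = 0.36.
- Between 0, within 0.5 (half acts through %fat): d is about -0.45, so the pooled slope is (0.50 - 0.45)/0.5 = 0.10.

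The bias is therefore not simply the share of the effect that acts through %fat.

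**5. Fat mass.** A change-score analysis (4,000 trials) assumed a true effect of -2.0 kg and an SD of change of 2 kg. It gave -2.0 kg (power 0.86) with baseline %fat, and about -0.3 kg (power 0.15) with the 16-week value added.

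**6. Which reading the text supports.** %fat is listed with three characteristics that the intervention cannot change. The list is illustrative, and the wording does not put every variable into every model. No section says that 16-week %fat will be a covariate.

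**The case for a change.** The strongest case for a change is that the text is silent where silence could be costly. %fat is the one listed variable that treatment can move, it is measured at both visits, and a choice made after seeing the data would be open to challenge. The separate document may not settle the matter, while a clarification would cost almost nothing. Even a reader who assumes baseline finds no instruction for %fat's own model.

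Much of this stands. The omission is real, and post-randomisation %fat would spoil the primary estimate. Three parts do not carry through. First, the plan itself places the covariate details in another document, so their absence from this paragraph does not show that they are undecided. Second, an exemption for %fat's own model is not essential on the baseline reading: step 2 shows that the estimate is unaffected, 7.3 offers the unstructured matrix only as an example, and an analyst who meets a singular fit would drop the redundant term. Third, the unadjusted t-tests do not leave open which result is read, because 7.3 names the mixed model as primary.

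**Conclusion.** No change to the plan follows. On its natural reading, section 7.3 gives a sound group-by-time estimate for every outcome. With complete data, baseline %fat changes the estimate by nothing beyond rounding, and in %fat's own model it is redundant. With incomplete data the exact identity need not hold, but a pre-randomisation covariate still does not absorb the effect of treatment.

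The possible harm is large only if an analyst enters 16-week %fat: about half of a -0.50 SD effect in one assumed case, none in another, and all of it when %fat is the outcome. Those sizes rest on assumed slopes and shifts that the documents do not supply. The conclusion rests on the baseline reading, which the list in 7.3 supports and no section contradicts. It would need another look only if the Rigor and Reproducibility document called for the post-randomisation value.

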8 SUPPORTING DOCUMENTATION AND OPERATIONAL CONSIDERATIONS

8.1 REGULATORY, ETHICAL, AND STUDY OVERSIGHT CONSIDERATIONS

8.1.1 INFORMED CONSENT PROCESS

- We will consent all participants in a private room with study personnel.

8.1.1.1 CONSENT/ASSENT AND OTHER INFORMATIONAL DOCUMENTS PROVIDED TO SUBJECTS

Consent forms describing in detail the study intervention, study procedures, and risks are given to the subject and written documentation of informed consent is required prior to conducting study screening procedures. A separate screening consent form will not be used.

8.1.1.2 CONSENT PROCEDURES AND DOCUMENTATION

Informed consent is a process that is initiated prior to the individual's agreeing to participate in the study and continues throughout the individual's study participation. Consent forms will be Institutional Review Board (IRB)-approved and the subject will be asked to read and review the document. The investigator will explain the research study to the subject and answer any questions that may arise. A verbal explanation will be provided in terms suited to the subject's comprehension of the purposes, procedures, and potential risks of the study and of their rights as research subjects. Subjects will have the opportunity to carefully review the written consent form and ask questions prior to signing. The subjects should have the opportunity to discuss the study with their family or surrogates or think about it prior to agreeing to participate. The subject will sign the informed consent document prior to any procedures being done specifically for the study. Subjects must be informed that participation is voluntary and that they may withdraw from the study at any time, without prejudice. A copy of the informed consent document will be given to the subjects for their records. The informed consent process will be conducted and documented in the source document (including the date), and the form signed, before the subject undergoes any study-specific procedures. The rights and welfare of the subjects will be protected by emphasizing to them that the quality of their medical care will not be adversely affected if they decline to participate in this study.

